PROTOCOL TITLE: Dedicated Breast PET/MRI in evaluation of disease in women with newly diagnosed breast cancer

PRINCIPAL INVESTIGATOR: [name] MD, Weill Cornell Medicine

IRB Protocol #: 1705018188

ClinicalTrials.gov Identifier: NCT03510988

Current Version: October 25, 2021

Prior Version Dates:

Version approved January 3, 2018

Version approved February 7, 2018

Version approved October 17, 2018

BACKGROUND

Despite advances in treatment, the stage at breast cancer diagnosis remains the most important factor in patient survival. Breast MRI is performed routinely as the mainstay in initial staging and evaluation of additional sites of ipsilateral and contralateral disease prior to oncologic/surgical management. Although the sensitivity of breast MRI is high, specificity is moderate and variable (1- 2), resulting in false positives which delay treatment and result in patient anxiety. Positron emission tomography provides functional and metabolic information that may improve specificity of detection. Recent literature suggests that fusing separately acquired Breast MRI and FDG-PET improves differentiation of benign versus malignant breast lesions, reducing the number of unnecessary biopsies (3-6). However, the potential of novel combined FDG PET/MRI performed simultaneously, which would decrease radiation to the patient, motion misregistration, and study acquisition time, has yet to be investigated.

3. Moy. L, Ponzo F, Noz ME, Maguire GQ, Murphy-Walcott AD, Deans AE, Kitazono MT, TRAvascio L, Kramer E. Improving specificity of Breast MRI using prone PET and Fused MRI and PET 3D Volume Datasets *J Nucl Med* April 2007 vol 48 (4) 528-537

Patient cohort and clinical question: This is a single institution study will involve women over age 25 with newly diagnosed breast cancer and for whom a breast MR has been ordered as standard of care will be recruited to undergo a hybrid dedicated Breast PET/MRI for evaluation of extent of disease prior to surgical and oncologic management. The study will investigate any incremental added benefit to breast MRI specificity by the addition of concurrent hybrid breast PET. Our hypothesis is that the combination of Breast PET/MRI, will improve specificity and decrease the number of false positive breast biopsies recommended based on breast MRI findings. Imaging modalities: The study will investigate a new technology of a hybrid 3T PET/MRI with a dedicated breast coil, capable of performing a dedicated breast PET/MRI. Patients with newly diagnosed breast cancer will be recruited to undergo a dedicated breast PET/MRI in lieu of standard of care breast MRI alone. The MRI portion of the PET/MRI will be read routinely by a clinical radiologist on service and given a BI-RADS followed by routine standard of care based on the BI-RADS assessment category. The PET portion of the hybrid PET/MRI will be archived to be used for research purposes only. Subjects will be informed of this in the informed consent. For purposes of the research study, all breast PET/MRIs will be anonymized and broken down into two components: a breast MRI component and the entire study with fused PET/MRI. This will be archived and stored on an IDEAL server. Several reading lists, or sessions, will be created from the archived studies containing 10 patients with a mixture of both the sole breast MRI component of the study for some patients as well as the entire reading session will include MRI only portion for patient A, the entire PET/MRI for patient B, MRI only portion for patient C, entire PET/MRI for patient D, etc, while second reading session presented to a reader will include the entire PET/MRI for patient A, MRI only portion for patient B, entire PET/MRI for patient C, MRI only portion for patient D etc). Readers in the study will be dedicated breast imagers, with prior experience in reading PET/CTs who will be blinded to clinical MRI reports as well as any follow up or pathology. After a reader training period of reading 10 breast PET/MRIs readers will be provided with at random a reading list/session of anonymized studies of breast PET/MRIs from the recruited cohort. Readers will be asked to provide a BIRADS as well as a likelihood of malignancy if BIRADS is greater than 2. After an extinguishing period of 6 weeks, they will read a different reading session PET/MRI portion of the study and provide BIRDAS and likelihood of malignancy if BIRADS is greater than 2. The gold standard will be pathology reports from any biopsies initiated by the breast MRI performed on the patients in this cohort. Negative and benign studies will be deemed true negatives after a period of 2 years without interval recurrence or a mastectomy specimen pathology report without additional sites of disease in addition to known index cancer. In addition, initial appropriate IV 18 F-FDG dosage will be evaluated by performing the first 10 breast PET/MRIs with different IV dosages of 18F-FDG as a pilot study. Routine whole-body PET/CT is performed with 0.15-0.19mCi/kg (approximately 10mCi of total dose for average weight patient), however counts are collected from at least 5 body stations spending approximately 4 minutes per body station. In our protocol, we will only be acquiring 18F-FDG

counts from the breasts, and since these are acquired for the duration of the breast MRI portion which takes 20 minutes, 20 minutes will be spent acquiring 18-F-FDG counts from the breasts, suggesting that a lower dosage of 18-F-FDG may be sufficient. *Please see attachments for continuation pages of study design section.

Primary Objective:

To assess the added benefit of breast FDG PET to the specificity of breast MRI performed on a hybrid dedicated simultaneous breast PET/MRI in patients with newly diagnosed breast cancer

Secondary Objective:

1. To assess the added benefit of FDG PET to MRI versus MRI alone performed on hybrid dedicated breast PET/MRI in various measures of accuracy (sensitivity, PPV, NPV)
2. To determine the optimal 18F-FDG dosage for a dedicated Breast PET/MRI
3. To assess whether decreased IV FDG dosage (than that used for whole body PET) may be used without compromising PET image quality (signal/noise ratio) while imaging the breast only
4. To explore the relationship of hybrid FDG PET/ MRI imaging features in prediction of breast cancer tumor biology (Estrogen/Progesterone and HER2 receptor status) both of the index cancer as well as the additional cancers diagnosed based on biopsy recommendations from the hybrid FDG PET/MRI
5. To explore the relationship of hybrid FDG PET/ MRI imaging features in prediction of breast cancer tumor recurrence (using a surrogate of Ki-67 and oncotyping when available) both of the index cancer as well as the additional cancers diagnosed based on biopsy recommendations from the hybrid FDG PET/MRI
6. To assess the added sensitivity of hybrid FDG PET/MRI in detection of axillary and internal mammary lymph node metastasis compared to MRI alone
7. To assess perceived patient benefit of undergoing a simultaneous FDG PET/MRI which may potentially decrease number of unnecessary biopsies (if our hypothesis that hybrid FDG PET/MRI has improved specificity over MRI alone holds true), decrease delays in surgery

Statistical Considerations:

1) Sample size: The primary endpoint is to evaluate the specificity by adding breast FDG PET to MRI compared with breast MRI alone for the diagnosis on patients with newly diagnosed breast cancer. Based on the results from previous studies, a specificity for PET/MRI of at most 60% will be considered as unacceptably low as it would provide little benefit over MRI alone. Hence, the null hypothesis that the specificity is 60% will be tested against the alternative hypothesis that the specificity is greater than 78%, i.e., an improvement of 30% on the original specificity. Therefore, a sample size of 42 breast biopsy negative subjects is required for rejecting the null hypothesis with 90% power at the one-sided 0.1 significance level. Given a general 20% positive biopsy rate, we will expect 11 biopsy positives resulting in 53 biopsy subjects. Eventually, with a 40% rate biopsy recommendation, we plan to recruit around 147 patients by allowing a 10% drop-off rate.

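### The second reading session is described as the same women with the modality swapped, with no re-mixing or re-ordering; any surviving recall would pull the paired specificity difference towards zero by an unknown amount

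*Combined protocol and SAP*

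**What the plan says.** The reading scheme is in the imaging modalities text under Study Design. On list size: "Several reading lists, or sessions, will be created from the archived studies containing 10 patients". On the first session, the "reading session will include MRI only portion for patient A, the entire PET/MRI for patient B", and so on through patients C and D. On the second session, the "second reading session presented to a reader will include the entire PET/MRI for patient A, MRI only portion for patient B", again continuing through C and D. The same women therefore return to the same reader with the modality reversed.

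The same text gives several safeguards. Studies are anonymised, lists are handed out at random, readers are blinded to clinical MRI reports, follow-up and pathology, and 6 weeks separate the reads. It also says that after the gap the reader takes a different session, and at that point it mentions only the PET/MRI part of the study.

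The statistical analysis section lists a paired McNemar test of specificity, PET/MRI against MRI alone, under the primary endpoint. The available pages do not describe re-mixing of women between lists, the order of cases in the second session, or any analysis of reading order.

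**The concern.** Both reads of a woman use the same MRI acquisition, so the images themselves can prompt recognition. Anonymisation and blinding to reports do not prevent that. If the ten women return as a set, recognising one distinctive case gives a cue to the others.

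A reader who remembers a case may repeat the earlier call. In a scheme balanced for order, that happens both ways: a PET/MRI call carried into a later MRI-alone read raises MRI-alone specificity, and an MRI-alone call carried into a later PET/MRI read lowers PET/MRI specificity. Both remove discordant pairs and move the paired difference towards zero. That difference is what answers the primary objective, the added benefit of PET to MRI specificity.

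Reading each woman twice is not the problem; the paired test requires it. The avoidable part is keeping the list intact and the cases in a fixed alternating pattern.

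**Working it through.** **Inputs from the sample size section.** "the null hypothesis that the specificity is 60% will be tested against the alternative hypothesis that the specificity is greater than 78"%, and "a sample size of 42 breast biopsy negative subjects is required for rejecting the null hypothesis with 90% power at the one-sided 0.1 significance level". The 18-point gap is 78 − 60, and 78/60 = 1.30, which matches the stated 30% improvement.

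**The plan's own figure.** One-sample proportion, normal approximation, z = 1.2816 for both one-sided 0.1 and 90% power:

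n = [(1.2816·√(0.60·0.40) + 1.2816·√(0.78·0.22)) / 0.18]² = 41.4, rounded up to 42.

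Then 42/0.8 = 52.5 (53 biopsied), 53/0.4 = 132.5, and 132.5/0.9 = 147.2 (about 147). All the stated figures reproduce. This calculation tests PET/MRI against a fixed 60%; it does not power the paired comparison.

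**Assumptions not in the documents.**
- MRI-alone specificity is 60% and PET/MRI 78%.
- A fraction r of all second reads repeats the first call.
- Half the women are read in each order.
- Reverse discordance (MRI alone correct, PET/MRI wrong) is 3% or 8% of negatives. Favourable discordance is then 18 + 3 = 21% or 18 + 8 = 26%.
- There is one pair of reads per woman, and McNemar is used one-sided at 0.1, as in the sample size section.

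**Effect on the difference.** MRI alone becomes 60 + 9r and PET/MRI becomes 78 − 9r, so the difference is 18 × (1 − r) points. Both discordant probabilities are multiplied by (1 − r).

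**Effect on McNemar power, 42 negatives.** Reject when (b − c)/√(b + c) ≥ 1.2816, without continuity correction, where b and c are the favourable and reverse discordant counts. Power is summed over the multinomial distribution.

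| r | Difference (points) | Power, 3% reverse | Power, 8% reverse |
|---|---|---|---|
| 0 | 18.0 | 91.3% | 79.6% |
| 10% | 16.2 | 89.2% | 75.8% |
| 20% | 14.4 | 86.7% | 71.6% |
| 30% | 12.6 | 83.6% | 67.2% |

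The closed-form approximation Φ[(d√n − z√ψ)/√(ψ − d²)], with d the difference and ψ the total discordance, is lower (88.1% at r = 0 and 77.2% at r = 30% with 3% reverse discordance) but shows the same pattern.

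**One direction only.** If only PET/MRI-first reads carried over into MRI alone, the difference would be 18 × (1 − r/2). At r = 30% that is 15.3 points, with power 88.0% (3% reverse) or 73.8% (8%).

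**The test against 60%.** Carry-over from PET/MRI into MRI alone leaves it unchanged, at 90.3% power by the normal approximation. Carry-over from MRI alone into PET/MRI lowers PET/MRI specificity to 77.1% (r = 10%) or 76.2% (r = 20%), and power to 87.4% or 83.9%.

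**The case against.** The plan already has the standard protections: a 6-week gap, anonymised studies, blinding, random allocation of lists, and modality order counterbalanced across women. Nothing in the documents shows that recall survives them. With about 147 women there would be roughly 15 lists, so a single list of ten is less memorable than it sounds. This stands: recall is a possibility, not a finding.

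The text is also unclear. The A-to-D pattern may be only an example, the sentence is broken in the available copy, and the later wording about a different session that names only PET/MRI could mean something other than the mirrored list. If every second read were PET/MRI, carry-over could run only from MRI alone to PET/MRI. The protocol also refers to continuation pages of the design section that are not available, so silence on case order is weak evidence. This lowers confidence, but a mirrored list is itself a different session, and the only composition actually described is the mirrored one.

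The most important objection concerns size. A reader might take the fall from 80% to 67% as the cost of this list scheme. It is not. The table compares total recall with none, under an assumed discordance. Re-mixing leaves the same reader seeing the same woman again, so recall of individual cases remains.

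A reader might also infer that PET information specifically contaminates the MRI-alone reads. In a counterbalanced scheme only about half of those reads follow a PET/MRI read, and the other half of the women are exposed to carry-over the opposite way. Nor does the predictability of the next modality add a bias of its own: the reader sees whether PET is present on opening the case, and knowing it earlier says nothing about the diagnosis.

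**Conclusion.** The point holds as a low-severity design refinement, with medium confidence. As described, the second session repeats the first list with modalities swapped, and no re-mixing, re-ordering or order analysis is given. If recall occurs, it biases the paired specificity difference towards no difference, so it could hide a benefit of PET but would not create one.

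The size cannot be derived from the documents. The ranges shown (18 down to 12.6 points; power 91% to 84%, or 80% to 67%) rest on assumed recall of up to 30% and assumed reverse discordance of 3% or 8%. They illustrate total recall over that range and are not the gain to be expected from re-mixing, which is some unknown part of it. The documents do not support a claim that recall will occur.

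**What to change.** For the session after the 6-week gap, redraw the women at random into new lists of 10 so that few share a list again. Randomise the case order and the modality sequence within each list. Keep the 6-week gap and the per-woman modality swap, so the paired analysis is unchanged. State this in the reading-session text, and make clear there that the second session contains both MRI-alone and PET/MRI reads if that is the intention.

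The cost is one new random list generated from the archive. No extra reads, readers or scans are needed.

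### Do the unstated BI-RADS cut-off and index-cancer rule leave the primary specificity undefined?

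*Combined protocol and SAP*

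**What the plan says.** The Study design section has dedicated breast imagers read the MRI component and the full PET/MRI in separate sessions. They are readers "who will be blinded to clinical MRI reports as well as any follow up or pathology", and the task is brief: "Readers will be asked to provide a BIRADS as well as a likelihood of malignancy if BIRADS is greater than 2". The Statistical analysis paragraph then computes specificity for each modality with Wilson intervals and compares them by McNemar's test. It does not define a positive call.

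The reference side says more. For biopsied findings: "The gold standard will be pathology reports from any biopsies initiated by the breast MRI performed on the patients in this cohort". For the remaining women the rule is different: "Negative and benign studies will be deemed true negatives", given two years free of recurrence or a mastectomy specimen "without additional sites of disease in addition to known index cancer". Secondary objectives 4 and 5 also separate the two kinds of cancer: "both of the index cancer as well as the additional cancers diagnosed based on biopsy recommendations".

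The sample-size paragraph counts biopsy-negative subjects. It assumes a 20% positive biopsy rate and a 40% biopsy recommendation rate. The Study design section ends with a pointer: "Please see attachments for continuation pages of study design section". Those pages are not among the supplied text.

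**The concern.** All participants have a known cancer, and the blinded readers are not told in the supplied text to exclude it, mask it or score it separately. If each woman receives one overall score, a reader who sees the index cancer and scores it correctly makes her test-positive. The reference standard looks only at additional disease, so a woman without any becomes a false positive on both modalities. Sensitivity moves the other way: a woman with additional disease is test-positive on the index call even if the additional site was missed.

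The cut-off is a second gap. A BI-RADS above 2 triggers the likelihood score but is not stated as the threshold for a positive read, so BI-RADS 3 could fall on either side. On this view two analysts could compute different primary results from the same reads.

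**Working it through.** **The plan's own figures.** Inputs from the Sample size paragraph: specificity 60% against 78%, one-sided 0.10, power 90%.

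- n = [(1.2816 × √(0.60 × 0.40) + 1.2816 × √(0.78 × 0.22)) / 0.18]² = 41.4, rounded up to 42, as stated.
- 42 / 0.80 = 52.5, so 53 biopsied; 53 − 42 = 11 positives.
- 53 / 0.40 = 132.5, and 132.5 / 0.90 = 147.2, the plan's figure of about 147.

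**Size of the problem if one score per woman counts the index.** Let d be the share of women whose index cancer is called. The documents do not give d, so it is a free parameter.

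- Bound: specificity ≤ 1 − d. It cannot exceed 78% once d = 1 − 0.78 = 22%, nor 60% once d = 1 − 0.60 = 40%.
- With index and other calls independent and a non-index specificity of 78%, apparent specificity is 0.78 × (1 − d). It equals 60% at d = 1 − 0.60/0.78 = 23%.
- Exact test with 42 women (reject at 30 or more, size 0.086): power 88.5% at d = 0, 50.7% at d = 10% (specificity 70.2%) and 14.7% at d = 20% (62.4%).
- If negative and benign studies also count as true negatives, the denominator is at most 147 × 0.90 − 11 = 121. Rejecting at 80 or more (size 0.099), power is 99.9%, 86.0% and 22.8%.
- At d of 80% to 100%, apparent specificity is 15.6% down to 0%.

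**Is that reading compatible with the plan?** Three checks say it is not.

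- Biopsy recommendation is planned for 40% of a cohort in which 100% have cancer: 147 × 0.90 × 0.40 = 52.9, the plan's 53. The planned positives are therefore findings other than the index.
- The plan treats 60% as the level that offers little over MRI alone. With the index counted, a specificity of 60% needs d ≤ 40%, so the index would go uncalled in at least 60% of women with a known cancer. No one would plan on that.
- If the index were counted in the reference as well, no woman would be disease-negative and specificity would have no denominator.

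Under per-lesion scoring the difficulty does not arise: the index is a true positive and does not enter specificity.

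**The paired comparison.** If both modalities make the same index call, those women are concordant and carry no weight in McNemar's test. Under independence the 18-point difference becomes 0.18 × (1 − d): 16.2 points at d = 10% and 10.8 at d = 40%. The direction is kept.

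**The cut-off.** Suppose specificity is 78% with BI-RADS 3 counted negative, and assume that 5%, 10%, 15% or 20% of reference-negative women are BI-RADS 3 (the documents give no share). Counting them positive gives 73%, 68%, 63% or 58%, and power with 42 women falls from 88.5% to 66%, 39%, 17% or 5%. The hypothesis in the Study design section concerns false-positive biopsy recommendations, and the exclusion criteria treat MRI-positive lesions as those to be biopsied. Both suggest that a positive read is one that leads to biopsy.

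**The case for a change.** The strongest case for acting is that intent inferred from the reference standard is not a reading form. A single score with no location cannot be split afterwards without reading the images again. A cut-off chosen after the reads are seen could decide the primary result, as the BI-RADS 3 figures show. Writing the rule down would need no extra patients or scans.

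Part of this stands. The supplied text does not state the cut-off, does not place BI-RADS 3 and does not tell readers what to do with the index.

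The rest is weaker:

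- No stated rule is shown to give a wrong answer. The damaging figures all need a woman-level score that counts the index against a reference that leaves it out, and the values d = 10% and 20% have no source in the documents.
- The blinding sentence covers clinical MRI reports, follow-up and pathology. It does not say that the index location is withheld.
- The BI-RADS category is itself recorded, so specificity can be computed with BI-RADS 3 on either side.
- If index handling proved unclear in completed reads, the images remain available: "This will be archived and stored on an IDEAL server".
- Reading rules would naturally sit in the continuation pages of the Study design section, so their absence from the plan cannot be established here.

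**Conclusion.** No change to the plan is needed. This is a gap in detail that the people doing the work would fill sensibly. The reference standard, the 40% biopsy recommendation rate and the 60% planning value all make sense only with the index cancer set aside, and dedicated breast imagers reading for extent of disease would score the other findings. Adding the rule would write down a definition and would not replace a stated method.

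The cap at 1 − d and the loss of power to 50.7% or 14.7% with 42 women are conditional on a reading that the documents point away from. The more realistic open item is BI-RADS 3. It could move specificity from 78% to between 73% and 58% for an assumed share of 5% to 20%, but the recorded categories let an analyst report either convention. The conclusion assumes that index handling and cut-off are the same for both modalities, which the paired design implies.

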Due to the risk profile of this study, we do not believe an interim analysis is necessary nor has the sample size been calculated to allow for an interim analysis. Secondary to alpha-spending, the sample size would have to be increased if an interim analysis were to take place. This increase in sample size is not justified given the lack of benefit to such an analysis.

The Data Safety Monitoring Board (DSMB) or Data Monitoring Committee (DMC) will not be utilized since it's not required. There are no therapeutic interventions. This study involves administration of trace amounts (micrograms) of radioactive drug FDG. No pharmacological effects can be observed at this mass level. 18F-FDG has been widely used for research and is approved by the FDA for routine clinical diagnostic studies.
